8.1. Ibrutinib Dose/Delays Modifications

8.1.1 Dose Modification for Adverse Reactions

The dose of ibrutinib must be modified according to the dose modification guidelines in the tables below if any of the following toxicities occur:

- Grade 4 neutropenia (ANC <500/ μ L) for more than 7 days. See Section 5.4 for instructions regarding the use of growth factor support.
- Grade 3 thrombocytopenia (platelets <50,000/ μ L) in the presence of clinically

significant bleeding events

- Grade 4 thrombocytopenia (platelets <25,000/ μ L).
- Grade 3 or 4 nausea, vomiting, or diarrhea if persistent, despite optimal anti-emetic and/or anti-diarrheal therapy.
- Any other Grade 4 or unmanageable Grade 3 toxicity.

For grade 3 and above cardiac arrhythmias, ibrutinib should be held. For grade 2 and above heart failure, ibrutinib should be held. If clinically indicated, the use of anticoagulants or antiplatelet agents may be considered for the thromboprophylaxis of atrial fibrillation.

If the dose of ibrutinib is reduced, at the investigator's discretion, the dose of ibrutinib may be re-escalated after 2 cycles of a dose reduction in the absence of a recurrence of the toxicity that led to the reduction. Dose changes must be recorded in the dose administration eCRF.

Dose delays and modifications will be made as indicated in the following table(s). The descriptions and grading scales found in the revised NCI Common Terminology Criteria for Adverse Events (CTCAE) version 5.0 will be utilized for dose delays and dose modifications. A copy of the CTCAE version 5.0 can be downloaded from the CTEP website

Table 10 Hematologic and Non-Hematologic Adverse Events

Occurrence	Action to be Taken
First	Hold Ibrutinib for Grade ≥ 3 neutropenia with infection/fever, or any Grade 4 hematological toxicities. Once the symptoms of the toxicity have resolved to Grade 1 or baseline, ibrutinib may be reinitiated. If these toxicities persist or recur following two dose reductions, ibrutinib will be discontinued
Non-Hematologic Adverse Events	
Occurrence	Action to be Taken
	Hold ibrutinib for Grade 2 cardiac failure. Hold Ibrutinib for any Grade 3 or greater non-hematological toxicities. Once the symptoms of the toxicity have resolved to Grade 1 or baseline, ibrutinib may be reinitiated. If these toxicities persist or recur following two dose reductions, ibrutinib will be discontinued

Table 11 Ibrutinib Dose Reduction Levels

Starting Dose Level	840 mg	560 mg	420 mg
Dose Reduction Level 1	560 mg	420 mg	280 mg
Dose Reduction Level 2	420 mg	280 mg	140 mg
Dose Reduction Level 3	280 mg	140 mg	Discontinue
Dose Reduction Level 4	140 mg	Discontinue	N/A

8.1.1.1 Leukocytosis/Leukostasis (Optional for ibrutinib Monotherapy study)

A high number of circulating white blood cells ($> 400,000/\mu\text{L}$) may confer increased risk of leukostasis; these subjects should be closely monitored. Administer supportive care such as hydration and/or leukapheresis as indicated. Ibrutinib may be temporarily held, and medical monitor should be contacted.

8.1.2 Dose Modification for Hepatic Impaired Subjects

Ibrutinib is metabolized in the liver and therefore subjects with clinically significant chronic hepatic impairment at the time of screening (Child-Pugh class B or C) are excluded from study participation.

- For subjects with existing chronic mild hepatic impairment (Child-Pugh class A) at enrollment, the starting dose has to be adjusted to a level of 280 mg daily.
- For subjects who develop mild hepatic impairment while on study (Child-Pugh class A), the recommended dose reduction for ibrutinib/placebo is to a level of 280 mg daily.
- For subjects who develop moderate to severe hepatic impairment while on study (Child-Pugh class B and C)
- Study drug will be held until resolved to mild impairment (Child-Pugh class A)

Subjects who develop acute hepatic toxicity with liver enzymes Grade 3 or higher while on study should be managed per standard dose modification guidelines.

Table 12 Dose Modification Guidelines for Hepatic Toxicity

Measure	1 point	2 points	3 points
Total bilirubin, $\mu\text{mol/L}$ (mg/dL)	$<34 (<2)$	34-50 (2-3)	$>50 (>3)$
Serum albumin, g/L (g/dL)	$>35 (>3.5)$	28-35 (2.8-3.5)	$<28 (<2.8)$
PT INR	<1.7	1.71-2.30	>2.30
Ascites	None	Mild	Moderate to Severe
Hepatic encephalopathy	None	Grade I-II (or suppressed with medication)	Grade III-IV (or refractory)

Points	Class
5-6	A
7-9	B

Source:

8.2. Lenalidomide, ibrutinib, and dexamethasone dose delay modifications

If treatment is held for more than 28 days, then all study treatment will be discontinued

Table 13 Lenalidomide, ibrutinib, and dexamethasone dose delay modifications

Neutropenia	Grade 3 or greater on day 1 of cycle: hold lenalidomide and monitor CBC weekly; if resolves to \leq grade 2 within 4 weeks, resume lenalidomide with 5mg dose reduction. During treatment, G-CSF or GM-CSF may be used after completion of cycle 1 for neutropenia at the discretion of as needed by the treating physician.
Febrile Neutropenia	Hold lenalidomide for the remainder of the cycle. Following completion of cycle 1, consider G-CSF administration until there is adequate count recovery ANC \geq 1000/ μ L + absence of fever. If neutropenia resolves \leq grade 2, resume with lenalidomide at 5 mg dose reduction for subsequent cycles
Thrombocytopenia	If grade 3 or greater, hold lenalidomide the remainder of the cycle and until platelets \geq 50,000/ μ L. Then resume lenalidomide at 5 mg dose reduction for subsequent cycles Platelet transfusion may be given following completion of cycle 1. Platelet transfusion for severe thrombocytopenia may be administered in cycle 1 at investigator discretion following discussion with Principal Investigators.
Anemia	For grade 3 or greater, hold lenalidomide for the remainder of the cycle and until hemoglobin recovers to \leq grade 2. Red cell transfusion may be given.
Fatigue (asthenia, malaise)	For intolerable grade 2 or grade 3-4, hold protocol therapy thought to be probable or definitely related to the reaction until resolves to \leq grade 1, then resume protocol therapy with dose reduction of implicated protocol therapy by one dose level (5 mg for lenalidomide, 1 dose level below for Ibrutinib and/or 50% for dexamethasone).
Rash	If grade 3 hold lenalidomide and ibrutinib until resolves to \leq grade 2, then resume protocol therapy. Antihistamine (Benadryl, Claritin, zyrtec) may be given. If grade \geq 3 rash recurs, hold therapy until rash resolves to \leq grade 2, resume with one level dose reduction of agent(s) believed to be responsible for rash. For grade 4 rash, exfoliative or bullous rash, Stevens-Johnson Syndrome, toxic epidermal necrolysis, drug reaction with eosinophilia and systemic symptoms (DRESS), permanently discontinue lenalidomide
Renal insufficiency	For patients with calculated or measured GFR <30 ml/min, lenalidomide should be omit until creatinine returns to baseline
Hepatic Toxicity	If Grade \geq 2, hold lenalidomide. After return to baseline, restart at 1 dose level below.

Venous Thromboembolism	All protocol treatment should be held until the patient is adequately anti-coagulated. Patients with recurrent thrombosis despite adequate anti-coagulation should be removed from protocol therapy.
Suspected Pregnancy	Protocol therapy should be held until pregnancy is ruled out. Discontinue all protocol therapy if pregnancy is positive
Dyspepsia, gastric or duodenal ulcer, gastritis Grade 1-2 (requiring medical management)	Treat with H2 blockers, sucralfate, or omeprazole. If symptoms persist despite above measures, decrease dexamethasone dose by 50%
Acute pancreatitis	Hold all study therapy until resolution. Do not resume dexamethasone. Consider one level dose reduction of either lenalidomide and/or ibrutinib.
Edema > Grade 3 (limiting function and unresponsive to therapy or anasarca)	Diuretics as needed and decrease dexamethasone dose by 50%; if edema persists despite above measures, decrease dose another dose level. Discontinue dexamethasone and do not resume if symptoms persist despite second reduction. Permanently discontinue lenalidomide for any episode of Angioedema
Confusion or mood alteration > Grade 2 (interfering with function ± interfering with activities of daily living)	Hold all study therapy until symptoms resolve. Restart with 50% reduction of dexamethasone. If symptoms persist despite above measures, permanently discontinue dexamethasone. Consider one level dose reduction of lenalidomide and/or ibrutinib if either agent is felt to be contributing.
Muscle weakness > Grade 2 (symptomatic and interfering with function ± interfering with activities of daily living)	Hold all study therapy. Restart with 50% dose reduction of dexamethasone dose. If weakness persists despite above measures decrease dose by another 50%. Discontinue dexamethasone and do not resume if symptoms persist. Consider one level dose reduction of lenalidomide and/or ibrutinib if either agent is felt to be contributing.
Hyperglycemia > Grade 3 or higher	Hold dexamethasone. Treat with insulin or oral hypoglycemics as needed. If uncontrolled despite above measures, decrease dose by 50%.

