1.4.2.9 Rash

Rash has been commonly reported in subjects treated with either single agent ibrutinib or in combination with chemotherapy. Most rashes were mild to moderate in severity. Isolated cases of severe cutaneous adverse reactions (SCARs) including Stevens - Johnson syndrome (SJS) have been reported in subjects treated with ibrutinib. Subjects should be closely monitored for signs and symptoms suggestive of SCAR including SJS. Subjects receiving ibrutinib should be observed closely for rashes and treated symptomatically, including interruption of the suspected agent as appropriate. In addition, hypersensitivity-related events erythema, urticaria, and angioedema have been reported.

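### For the most severe rashes, Table 13 permanently stops lenalidomide only and leaves ibrutinib to general rules that can allow it to be given again

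*Combined protocol and SAP*

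**What the plan says.** The rash row of Table 13 (Section 8.2) has two parts that matter here.

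- For Grade 3 rash it names both drugs: "If grade 3 hold lenalidomide and ibrutinib until resolves to" Grade 2 or lower, after which protocol therapy resumes.
- For the most severe forms it names one drug: "For grade 4 rash, exfoliative or bullous rash, Stevens-Johnson Syndrome, toxic epidermal necrolysis, drug reaction with eosinophilia and systemic symptoms (DRESS), permanently discontinue lenalidomide".

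Section 1.4.2.9 ties the same class of reaction to ibrutinib: "Isolated cases of severe cutaneous adverse reactions (SCARs) including Stevens - Johnson syndrome (SJS) have been reported in subjects treated with ibrutinib". It asks for close monitoring and for interruption of the suspected agent as the investigator sees fit.

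Otherwise ibrutinib is governed by Section 8.1.1. "The dose of ibrutinib must be modified according to the dose modification guidelines in the tables below" when a listed toxicity occurs, and the list includes "Any other Grade 4 or unmanageable Grade 3 toxicity". Table 10 holds ibrutinib for non-hematologic toxicity of Grade 3 or higher. It then says: "Once the symptoms of the toxicity have resolved to Grade 1 or baseline, ibrutinib may be reinitiated". Its only compulsory stop is: "If these toxicities persist or recur following two dose reductions, ibrutinib will be discontinued".

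**The concern.** Stevens-Johnson syndrome (SJS), toxic epidermal necrolysis (TEN) and drug reaction with eosinophilia and systemic symptoms (DRESS) can be fatal. When one occurs on a combination, either drug may be the cause. The protocol treats them as an absolute bar to further lenalidomide. It also states that severe cutaneous reactions including SJS have been seen with ibrutinib, yet it sets no matching bar for ibrutinib. A site could give ibrutinib again after such a reaction and still be following the protocol. What is at stake is the safety of the individual patient.

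**Working it through.** The plan gives no figure to reproduce. The check is to follow each kind of reaction in the last sentence of the rash row through every rule that could govern ibrutinib.

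| Reaction | Lenalidomide | Ibrutinib |
|---|---|---|
| Grade 4 (any listed form) | Permanent stop (Table 13) | Held (Table 10); may restart at Grade 1 or baseline |
| Grade 3 SJS, TEN, DRESS, exfoliative or bullous rash | Permanent stop (Table 13) | Held (Table 10 and Table 13); Table 10 allows restart at Grade 1 or baseline, while the Table 13 Grade 3 sentence resumes therapy at Grade 2 or lower |
| Exfoliative or bullous rash below Grade 3 | Permanent stop (Table 13) | No hold stated: below the Table 10 threshold, the Section 8.1.1 triggers and the Table 13 Grade 3 sentence |

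**Is the omission of ibrutinib only loose wording?** Probably not. The same row names ibrutinib for Grade 3 rash. Other Table 13 rows refer to all study or all protocol therapy when they mean it, for example acute pancreatitis and a positive pregnancy test. A site will read the last sentence as applying to lenalidomide alone.

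**Do other rules close the gap?**

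- Section 8.2 ends all treatment if it is held for more than 28 days, and Section 8.3 does so for a delay over 4 weeks. Neither reaches a reaction that settles sooner.
- Section 8.3 ends therapy for adverse events judged unacceptable. The term is not defined, and Section 1.2 and the synopsis leave open re-treatment at a lower dose after unacceptable toxicity.
- Section 6.2 lets a new cycle start once drug-related hypersensitivity is at Grade 1 or lower, and other drug-related events at Grade 2 or lower. It makes no exception for severe skin reactions.

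**When does Table 10 itself force a stop?** After two reductions. From Table 11, "Dose Reduction Level 2" is reached as 560 → 420 → 280 mg (280/560 = 50%) for dose levels 1 and 2, and as 840 → 560 → 420 mg (420/840 = 50%) for dose level 3. Table 10 alone therefore requires no stop until toxicity persists or recurs at half the starting dose.

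**How often might it arise?** The documents describe isolated cases and give no rate. As an assumption only, take a per-patient risk p of a severe cutaneous reaction between 0.1% and 1%. The chance of at least one among N patients is 1 − (1 − p)^N.

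- N = 19: 1 − 0.999^19 = 1.9%; 1 − 0.99^19 = 17.4%.
- N = 25: 1 − 0.999^25 = 2.5%; 1 − 0.99^25 = 22.2%.

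These are chances of any severe cutaneous reaction. The chance of one followed by an ibrutinib restart is smaller, and the documents do not allow it to be estimated.

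**The case against.** The strongest reply is that existing safeguards leave only a narrow opening. Few investigators would call SJS or TEN acceptable, and Section 8.3 then ends therapy. Section 1.4.2.9 already asks for close monitoring and interruption of the suspected agent. A serious reaction is reported within 24 hours (Section 10.5.5), and the DSMB reviews safety twice a year (Section 15.12). Table 13 also stops only lenalidomide for angioedema, although Section 1.4.2.9 lists angioedema with ibrutinib. That looks like a deliberate set of lenalidomide rules rather than a slip. The Investigator's Brochure, which the protocol cites for safety detail, may advise on this and cannot be seen here.

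Much of this stands as a limit on size. It does not close the gap: reporting and review do not forbid a restart, the unacceptable-event criterion rests on judgment, and a lenalidomide rule does not say what to do with ibrutinib.

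Three stronger readings are tempting and should be resisted.

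- A reader might infer that the protocol orders ibrutinib to be restarted after every such reaction. Table 10 only permits it. The Grade 3 sentence in Table 13 does say to resume, but it speaks of Grade 3, and Section 8.3 remains available.
- A reader might infer that the Table 10 route covers every reaction listed. It does not reach exfoliative or bullous rash below Grade 3, where the problem is that no hold is stated.
- A reader might take 2% to 22% as the probability of harm. It rests on an assumed rate and concerns any severe cutaneous reaction. Nine patients were already accounted for by October 2021 (six counted at dose level 1 in Section 14.1, three at dose level 2 in Section 7.3). That left 10 to 16 to enrol, plus anyone still on treatment, whom an amendment could protect.

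**Conclusion.** The point holds. For the most severe rashes the protocol permanently stops lenalidomide only, and no provision requires ibrutinib to stop because of the reaction itself. For Grade 3 or higher, ibrutinib can be given again if the hold is 28 days or less and the investigator does not end therapy for an unacceptable event. Below Grade 3, exfoliative or bullous rash triggers no stated hold.

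The event is rare and its rate is not given, so the point rests on severity rather than frequency. It is a patient-safety matter and worth correcting. It does not touch the analyses: a treatment-related non-hematologic reaction of Grade 3 or higher in cycle 1 already counts as a DLT (Table 9) whether or not ibrutinib is resumed, and the response rate uses all patients who began treatment (Section 14.3.2). Confidence is medium, because the Investigator's Brochure was not available.

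**What to change.** Replace the last sentence of the Table 13 rash row with:

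> For SJS, TEN or DRESS, permanently discontinue lenalidomide and ibrutinib. For exfoliative or bullous rash or other Grade 4 rash, permanently discontinue lenalidomide and hold ibrutinib; permanently discontinue ibrutinib unless the event is assessed as unrelated or unlikely related to ibrutinib (Section 10.6.2). This overrides the Grade 3 resume rule in this row, the Table 10 restart provision, and the lower-dose re-treatment provision in Section 1.2 and the synopsis.

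The attribution exception avoids ending ibrutinib for a mild bullous rash with another clear cause. Section 10.6.2 assigns the possibly related category when the product is one of several plausible causes, so an event that either drug could have caused would still lead to a stop.

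The cost is one table entry, with no added visits, tests or patients. Section 15.7 allows an operational memo ahead of a formal amendment where patient safety is concerned. The downside is that an occasional patient loses ibrutinib when lenalidomide was the cause.

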8.2.1 Ibrutinib Dose Modifications for Use with CYP3A Inhibitors

The coadministration of ibrutinib with a strong or moderate CYP3A inhibitor may increase ibrutinib plasma concentrations. Increased ibrutinib concentrations may increase the risk of drug-related toxicity. Dose modifications of ibrutinib are recommended when used concomitantly with posaconazole, voriconazole and moderate CYP3A inhibitors.

Table 14 Recommended dose modifications for ibrutinib

Patient Population	Coadministered Drug	Recommended Ibrutinib Dose
B-Cell Malignancies	• Moderate CYP3A inhibitors	280 mg once daily Interrupt dose as recommended (see label)

	
• Voriconazole 200 mg twice daily• Posaconazole suspension 100 mg once daily, 100 mg twice daily, or 200 mg twice daily	140 mg once daily Interrupt dose as recommended (see label)
B-Cell Malignancies	
• Posaconazole suspension 200 mg three times daily or 400 mg twice daily• Posaconazole IV injection 300 mg once daily• Posaconazole delayed-release tablets 300 mg once daily	70 mg once daily Interrupt dose as recommended (see label)
	
• Other strong CYP3A inhibitors	Avoid concomitant use. If these inhibitors will be used short-term (such as anti-infectives for seven days or less), interrupt ibrutinib

8.3. Criteria for Discontinuation of Protocol treatment

Patients are continued on treatment until any of the criteria for discontinuation of protocol therapy is met, which includes:

- Tumor progression
- Request by the patient to withdraw
- Unacceptable adverse events
- Treatment delay of >4weeks
- Intercurrent illness which would, in the judgment of the investigator, affect assessments of clinical status to a significant degree or require discontinuation of drug

Administration of non-protocol anti-tumor drug during the trial. Patients who discontinue treatment for any of the above reasons will go to survival follow-up where late toxicities and clinical outcome information will be collected every 6 months for a maximum of 2 years post registration. Once a patient has entered the survival follow-up phase of the trial, his/her therapy is at the discretion of the treating physician.

9. Study Assessments and Procedures

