	
there are no other higher dose levels to be tested, this will be considered the MTD.
 
Patients will return to the clinic every 28 days for physical exams, laboratory assessments and review of side effects.
 
Patients who do not have disease progression and have not experienced unacceptable toxicities will be eligible to continue protocol treatment at their current dose level until disease progression, unacceptable toxicity, or refusal. Those patients who have not experienced progression of disease but have unacceptable toxicity may be eligible for re-treatment at a lower dose.
 
Part 2: Dose Expansion Once the MTD has been established or determined, 4-10 additional patients will be treated at the MTD of lenalidomide and ibrutinib at the same schedule as above. Dexamethasone will be given at the same dose as in the dose escalation portion of the study.
 
Patients who have not had disease progression and have experienced acceptable toxicity will be eligible to continue protocol treatment at their current dose level until disease progression, unacceptable toxicity, or refusal. Those patients who have not progressed and who have experienced unacceptable toxicity may be eligible for re-treatment at a lower dose. A maximum of 2 reductions are allowed.
 
Criteria for discontinuation of protocol therapy include:
 
• Tumor progression• Request by the patient to withdraw• Unacceptable adverse events• Treatment delay of >4weeks• Intercurrent illness which would, in the judgment of the investigator, affect assessments of clinical status to a significant degree that require discontinuation of drug• Non-protocol chemotherapy, or an experimental drug during the trial 
Patients who discontinue treatment for any of the above reasons will go to survival follow-up. Once a patient has entered the survival follow-up phase of the trial, his/her therapy is at the discretion of the treating physician. Patients' charts will be reviewed for progression and survival endpoints during visits with treating physicians.
 
Bone marrow aspirate will be collected at pre-treatment and at end of cycle 1 for micro-RNA profiling and gene expression for correlative studies.
 
Peripheral blood will be collected at pre-treatment, after cycles 1, 3, 6 and 12 for immunome correlative studies.

--	---

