9.1.5 Follow-up for Other Malignancies

Occurrences of any new malignant tumors including solid tumors, skin malignancies and hematologic malignancies will be reported throughout study participation, including duration of study treatment and during any protocol specified follow-up periods.

Table 15 **Schedule of Assessment**

Treatment Day → Assessments and Procedures ↓	≤ 14 days prior to registration	Day 1 (all cycles)	Day 15 ± 2 days (all cycles)	End of Cycle 1	End of Cycle 3	End of Cycle 6	At end of treatment or treatment discontinuation
History and exam, weight ^a	X	X	X				X
Height	X						
ECOG Performance Status	X	X	X				X
Adverse event assessment	X	X	X				X
Concomitant Medications	X						X
Hematology group: WBC, ANC, ALC, Hgb, and PLT ^b	X	X	X				X
Chemistry group SGOT AST, total bili, Alk Phos, Creatinine, potassium, calcium, magnesium, phosphorus, sodium, albumin), blood glucose ^b	X	X	X				X
TSH, Free T4 ^{cc}	X						
LDH, Uric Acid ^b	X	X	X				X
Serum pregnancy test ^d	X						
Complete body CT	X	X ^e				X ^e	X ^e
Bone Marrow Biopsy ^f	X			X			
Mandatory blood specimens ^g	X	X ^g		X ^g	X ^g	X ^g	
ECG ^h	X						X

Treatment Day → Assessments and Procedures ↓	≤ 14 days prior to registration	Day 1 (all cycles)	Day 15 ± 2 days (all cycles)	End of Cycle 1	End of Cycle 3	End of Cycle 6	At end of treatment or treatment discontinuation
Serum Immunoglobulins, monoclonal protein and free light chain; beta 2 microglobulin ⁱ	X						X

- a. History, exam, and weigh will be done on day 1 of subsequent cycles after cycle 2
- b. Labs will be done weekly for the first 2 cycles, then on day 1 of subsequent cycles
- c. TSH and Free T4 at screening and every 2 cycles
- d. To be performed within 7 days of receiving drug.
- e. If clinically indicated for those with extramedullary disease indicated on baseline CT at completion of cycle 6 (cycle 6 day 28 ±3 days) or to confirm CR
- f. 2 tubes of 5 ml each of bone marrow aspirates in green tube (2) to be collected pre-treatment (prior to start of cycle 1) and at end of cycle 1 (prior to start of cycle 2).
- g. 15 ml peripheral blood to be collected prior to start of treatment and at end of cycles 1, 3, and 6 for the immunome correlate
- h. ECG should be performed within 14 days prior to registration and end of treatment, and as needed during the course of the study.

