- i. Immunoglobulins, serum free light chains (kappa and Lambda), serum monoclonal protein, beta 2 microglobulin ≤ 14 days prior to registration and day 1 of each cycle. 24-hour Urine Protein and immunofixation ≤ 14 days prior to registration, and every 3 months.

10. Adverse Events

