14.3.1 Statement for Secondary Endpoints

Secondary Endpoints include:

Maximum Toxicity Grade:

The maximum grade of each type of toxicity will be recorded for each patient. For each toxicity reported by dose level, the percentage of patients developing any degree of that toxicity as well as the percentage of patients developing a severe degree (Grade 3 or higher) will be determined.

Number/Duration of Response:

For each dose level, the number of response and the duration of response will be tabulated. The duration of response is the time from initiation of first response to first documentation of disease

progression or death. Patients who have not progressed will be censored at the date of their last disease evaluation.

Progression-free Survival (PFS)/ Overall Survival (OS)

Secondary endpoints for the expansion cohort include progression-free survival (PFS) and overall survival (OS) time.

Survival time is defined as the time from study entry to death due to any cause.

Progression-free survival time is the time from study entry to the documentation of disease progression or death due to any cause.

If a patient dies without a recurrence documented, the patient will be censored at the date of last disease evaluation. The distribution of response times, progression-free survival times and survival times will be estimated using the Kaplan-Meier method.

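### No disease-assessment schedule or progression-dating rule applies after a stop for a reason other than progression, so PFS and duration of response may be overstated by an uncertain amount

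*Combined protocol and SAP*

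**What the plan says.** **On treatment.** Table 15, footnote i, schedules immunoglobulins, FLC and "serum monoclonal protein, beta 2 microglobulin ≤ 14 days prior to registration and day 1 of each cycle". Urine is less frequent: "24-hour Urine Protein and immunofixation ≤ 14 days prior to registration, and every 3 months". CT is done only if clinically indicated (Section 9.1.1).

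**After treatment.** The last column of Table 15 is "At end of treatment or treatment discontinuation", and there is no follow-up column. Section 8.3 lists progression, patient request, unacceptable adverse events, a delay over 4 weeks, intercurrent illness and non-protocol anti-tumor therapy as reasons to stop, and then says: "Patients who discontinue treatment for any of the above reasons will go to survival follow-up". In that phase "late toxicities and clinical outcome information will be collected every 6 months for a maximum of 2 years post registration". The Synopsis adds that patients' "charts will be reviewed for progression and survival endpoints during visits with treating physicians". Neither place gives a visit interval or names the tests to be done.

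**Endpoints.** Under Section 14.3.1 (Statement for Secondary Endpoints), "Progression-free survival time is the time from study entry to the documentation of disease progression or death due to any cause". Duration of response likewise runs to the first documented progression or death. PFS and OS are named there for the expansion cohort, and duration of response is tabulated by dose level. The same section also says: "If a patient dies without a recurrence documented, the patient will be censored at the date of last disease evaluation".

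**The concern.** The endpoints stay open after the assessments that define them have stopped. A patient who stops for toxicity, delay, illness or by choice leaves the per-cycle serum schedule without having progressed, and no protocol-defined testing replaces it. Because the event date is the date of documentation, sparser testing can only move a captured progression later. No rule says whether the date to use is that of the laboratory test in the chart or that of the 6-monthly contact, and none covers new anti-myeloma therapy begun before progression.

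The death rule pushes the same way. A patient who stops, progresses unobserved and then dies is censored, although the PFS definition counts the death as an event.

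At stake is how far PFS and duration of response can be trusted in a small single-arm study, where they can only be read against outside results obtained under other assessment schedules.

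**Working it through.** The plan states no PFS or duration-of-response target, so there is no figure to reproduce. The check is how large the effect could be.

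**Inputs from the documents**
- On-treatment serum interval: 28 days, or 28/30.4375 = 0.92 month.
- Off-treatment collection interval: 6 months, ending 24 months after registration (Section 8.3).
- Illustrative medians: 5 months (event-free survival in patients refractory to lenalidomide and bortezomib, Section 1.1.3) and 11.1 months (time to progression on lenalidomide plus dexamethasone, Table 1).

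**Assumptions**
- Either median could apply to this trial.
- 10% to 40% stop before progressing. Section 1.1.2.2 reports 6 adverse-event discontinuations in an earlier ibrutinib study, without a denominator, so it does not fix this share.
- Off-treatment progression is detected on a 3-month grid (plausible clinic visits) or a 6-month grid (worst case), counted from the stop date.
- Times are exponential, and stopping is independent of progression.

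**Step 1: lag per affected patient.** As a rule of thumb, mean lag is half the interval: 0.92/2 = 0.46 month on the 28-day schedule, 1.5 months at 3-monthly testing and 3.0 months at 6-monthly. For exponential times with hazard λ = ln 2/median and interval g, the mean lag is g/(1 − exp(−λg)) − 1/λ.
- Median 5, g = 6: λ = 0.1386, so 6/0.5647 − 7.21 = 3.4 months.
- Median 11.1, g = 6: λ = 0.0624, so 6/0.3125 − 16.01 = 3.2 months.
- Median 5, g = 0.92: 0.92/0.1197 − 7.21 = 0.47 month.

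A simulation of 400,000 patients per scenario gives the same lags, and 1.5 to 1.6 months on the 3-month grid. The excess over the 28-day schedule is about 2.5 months by the half-interval rule (3.0 − 0.46) and up to about 2.9 months simulated (3.4 − 0.47).

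**Step 2: Kaplan-Meier estimates.** Same simulation, with off-treatment follow-up cut at 24 months. Each cell shows the 28-day / 3-month / 6-month off-treatment grid.

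| True median (months) | Stop first | Median PFS (months) | 12-month PFS (%) |
|---|---|---|---|
| 5 | 10% | 5.5 / 5.5 / 5.5 | 19.2 / 19.9 / 20.9 |
| 5 | 20% | 5.5 / 5.5 / 6.3 | 19.5 / 20.7 / 22.7 |
| 5 | 30% | 5.5 / 5.5 / 6.4 | 19.6 / 21.3 / 24.7 |
| 5 | 40% | 5.5 / 5.9 / 6.7 | 19.8 / 22.2 / 26.8 |
| 11.1 | 10% | 12.0 / 12.0 / 12.0 | 47.4 / 47.7 / 48.1 |
| 11.1 | 20% | 12.0 / 12.0 / 12.0 | 47.6 / 48.1 / 49.1 |
| 11.1 | 30% | 11.8 / 12.0 / 12.2 | 47.8 / 48.6 / 50.2 |
| 11.1 | 40% | 11.7 / 12.0 / 12.9 | 48.0 / 49.2 / 51.5 |

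Before rounding, the largest median shift is 6.73 − 5.52 = 1.2 months on the 6-month grid and 5.855 − 5.520 = 0.3 month on the 3-month grid. Twelve-month PFS rises by 0.7 to 7.0 points on the 6-month grid and by 0.3 to 2.4 points on the 3-month grid. On-treatment events fall on cycle boundaries, so the median moves in steps and can stand still while the curve rises.

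**Step 3: the 2-year limit.** On the 6-month grid, 2% to 5% of all patients (median 5) or 6% to 21% (median 11.1) have a progression that falls beyond the limit. They are censored rather than dated late.

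**Step 4: precision.** With 10 events and an exponential median of 5 months, the 95% interval runs from 2 × 10 × 5/34.17 = 2.9 to 2 × 10 × 5/9.59 = 10.4 months (chi-square quantiles, 20 degrees of freedom).

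**The case against.** The strongest reply is that six months is how often information is collected, not how often disease is tested. A chart read at month 6 can supply a test result from month 2, and if treating physicians test every 4 weeks there is no lag. This stands. A reader might infer that off-treatment progressions will be dated at 6-monthly contacts and that PFS is therefore overstated. The documents do not say so; they leave the dating rule open.

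A reader might also infer that the bias favours the less tolerable dose, since toxicity stops depend on dose. That is not supported for PFS, which Section 14.3.1 names only for the expansion cohort, treated at a single dose level. Duration of response is listed by dose level, but descriptively, and the MTD rests on cycle 1 DLTs.

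Other limits also stand:
- The 28-day interval covers serum markers only.
- Patients with unacceptable toxicity may be re-treated at a lower dose (Synopsis, Section 1.2), so many may stay on schedule.
- Section 3.1 says patients should not have progressed on lenalidomide above 10 mg, so the 5-month figure comes from a population that is largely excluded.
- Sampling error in 4 to 10 expansion patients (Synopsis) far exceeds any shift shown.

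None of this supplies the missing schedule or dating rule. Section 13.4 asks for one method and technique throughout the study but sets no interval after treatment. Wide sampling error does not remove a one-directional shift.

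**Conclusion.** The gap is real: after a stop without progression, the plan has no disease-assessment schedule and no rule for dating progression, while PFS and duration of response remain open. Captured progressions can only move later, and some may be missed, so overstatement is possible but not established. Under the stated assumptions the shift in median PFS is 0 to about 0.3 month with roughly 3-monthly testing. It reaches about 1.2 months only with dating at 6-monthly contacts and 40% stopping first; at 10% stopping the median does not move on either grid. Deaths and informative stopping were not modelled. These are secondary endpoints, no dose decision rests on them, and the change is worth making because it is cheap.

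**What to change.** **Section 8.3 and Table 15.** Add a follow-up column for patients who stop without progression. Record serum M-protein and FLC at the cycle interval and urine at its existing 3-monthly interval, accepting standard-of-care results, until progression, death or new anti-myeloma therapy. State how the 2-year limit applies to this follow-up. Keep the 6-monthly contact for survival.

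**Section 14.3.1 (Statement for Secondary Endpoints).**
- Date progression by the test that shows it, not by the contact at which it is collected.
- Add a PFS sensitivity analysis that censors at the last on-schedule disease evaluation, and state that it assumes stopping is non-informative. That is open to doubt for toxicity stops, so it supplements the main analysis.
- Reconcile the rule that censors deaths without documented recurrence with the definition that counts death as a PFS event.

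**Cost.** A protocol and eCRF amendment, a few laboratory entries for a minority of at most 25 patients (Section 14.2), and one more Kaplan-Meier run. No treatment rule changes.
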